10.1.8 Data Quality Assurance

All participant data relating to the study will be recorded on printed or electronic CRF unless transmitted to the Sponsor or designee electronically (eg, laboratory data). The investigator or qualified designee is responsible for verifying that data entries are accurate and correct by physically or electronically signing the CRF.

Detailed information regarding Data Management procedures for this protocol will be provided separately.

The investigator must maintain accurate documentation (source data) that supports the information entered in the CRF.

The investigator must permit study-related monitoring, audits, IRB/IEC review, and regulatory agency inspections and provide direct access to source data documents.

Study documentation will be promptly and fully disclosed to the Sponsor by the investigator upon request and also shall be made available at the study site upon request for inspection, copying, review, and audit at reasonable times by representatives of the Sponsor or any regulatory authorities. The investigator agrees to promptly take any reasonable steps that are requested by the Sponsor or any regulatory authorities as a result of an audit or inspection to cure deficiencies in the study documentation and worksheets/CRFs.

The Sponsor or designee is responsible for the data management of this study including quality checking of the data.

Study monitors will perform ongoing source data review and verification to confirm that data entered into the CRF by authorized site personnel are accurate, complete, and verifiable from source documents; that the safety and rights of participants are being protected; and that the study is being conducted in accordance with the currently approved protocol and any other study agreements, ICH GCP, and all applicable regulatory requirements.

Records and documents, including participants' documented informed consent, pertaining to the conduct of this study must be retained by the investigator for 15 years after study completion unless local regulations or institutional policies require a longer retention period. No records may be destroyed during the retention period without the written approval of the Sponsor. No records may be transferred to another location or party without written notification to the Sponsor.

10.1.9 Source Documents

Source documents provide evidence for the existence of the participant and substantiate the integrity of the data collected. The investigator/institution should maintain adequate and accurate source documents and study records that include all pertinent observations on each of the site's participants. Source documents and data should be attributable, legible, contemporaneous, original, accurate, and complete. Changes to source data should be traceable, should not obscure the original entry, and should be explained if necessary (eg, via an audit trail). Source documents are filed at the investigator's site.

Data reported on the CRF or entered in the eCRF that are transcribed from source documents must be consistent with the source documents or the discrepancies must be explained. The investigator/institution may need to request previous medical records or transfer records, depending on the study. Also, current medical records must be available.

10.1.10 Study and Site Closure

The Sponsor or its designee may stop the study or study site participation in the study for medical, safety, regulatory, administrative, or other reasons consistent with applicable laws, regulations, and GCP.

In the event the Sponsor prematurely terminates a particular study site, the Sponsor or designee will promptly notify that study site's IRB/IEC as specified by applicable regulatory requirement(s).

10.2 Appendix 2: Clinical Laboratory Tests

- The tests detailed in the table below will be performed by the local laboratory.
- Protocol-specific requirements for inclusion or exclusion of participants are detailed in Section 5 of the protocol.
- Additional tests may be performed at any time during the study as determined necessary by the investigator or required by local regulations.
- Pregnancy testing:
 - Pregnancy testing requirements for study inclusion are described in Section 5.1.
 - Pregnancy testing (urine or serum as required by local regulations) should be conducted at the end of relevant systemic exposure.
 - Additional serum or urine pregnancy tests may be performed, as determined necessary by the investigator or required by local regulation, to establish the absence of pregnancy at any time during the subject's participation in the study.

Protocol-required Safety Laboratory Assessments

Hematology	Comprehensive Chemistry Panel	Urinalysis	Other
Hematocrit	Albumin	Blood	Pregnancy test (serum or urine) ^a
Hemoglobin	Alkaline phosphatase	Glucose	Total T3 (or Free T3 [FT3]), Total T4 (or Free T4 [FT4]), and TSH ^{b,c}
Platelet count	Alanine aminotransferase	Protein	Anti-HCV ^e
WBC (total and differential) ^d	Aspartate aminotransferase	Specific gravity	HCV viral load ^{c, e}
RBC	Carbon dioxide or bicarbonate	Microscopic examination, if abnormal results are noted	HIV Viral Load, HIV 1,2 Antibody ^{e, f}
Absolute lymphocyte count ^d	Calcium		anti-HBs ^{c, e}
	Chloride		HbsAg
Absolute neutrophil count ^d	Creatinine		anti-HBc (total and IgM) ^{c, e}
PT/INR	Glucose		HbeAg ^{c, e}
PTT or aPTT	Phosphorus		anti-Hbe ^{c, e}
Basophil	Potassium		HBV viral load ^{c, e}
Eosinophil	Sodium		CD4+ T-cell count ^f

Hematology	Comprehensive Chemistry Panel	Urinalysis	Other
Monocyte	Total bilirubin		
	Direct bilirubin		
	Total protein		
	Blood urea nitrogen		
	Urea		
	Lactate dehydrogenase		

aPTT=activated partial thromboplastin time; HBc=hepatitis B core; HBeAg=hepatitis B e-antigen; HBsAg=hepatitis B surface antigen; HBV=hepatitis B virus; HCV=hepatitis C virus; HIV=human immunodeficiency virus; INR=International Normalized Ratio; PT=prothrombin time; PTT=partial thromboplastin time; RBC=red blood count; T3=triiodothyronine; T4=thyroxine; TSH=thyroid-stimulating hormone; WBC=white blood count.
 
^a Perform on women of childbearing potential only 72 hours prior to Day 1 of Cycle 1. Pregnancy tests must be repeated prior to every cycle if required or as specified per local regulatory guidance.
 
^b T3 is preferred; if not available, Free T3 may be tested.
 
^c If the local laboratory is unable to perform these tests, the site should submit the sample to the central laboratory for testing. Details are provided in the Laboratory Manual.
 
^d Report % or absolute results per standard of practice. Report the results in the same manner throughout the study.
 
^e Only collect if consistent with local requirements.
 
^f For HIV-positive participants only
			

The investigator (or medically qualified designee) must document their review of each laboratory safety report.

10.3 Appendix 3: Adverse Events: Definitions and Procedures for Recording, Evaluating, Follow-up, and Reporting

10.3.1 Definitions of Medication Error, Misuse, and Abuse

Medication error

This is an unintended failure in the drug treatment process that leads to or has the potential to lead to harm to the patient.

Misuse

This refers to situations where the medicinal product is intentionally and inappropriately used not in accordance with the terms of the product information.

Abuse

This corresponds to the persistent or sporadic, intentional excessive use of a medicinal product for a perceived psychological or physiological reward or desired nontherapeutic effect.

10.3.2 Definition of AE

AE definition

- An AE is any untoward medical occurrence in a clinical study participant, temporally associated with the use of study intervention, whether or not considered related to the study intervention.
- NOTE: An AE can therefore be any unfavorable and unintended sign (including an abnormal laboratory finding), symptom, or disease (new or exacerbated) temporally associated with the use of a study intervention.
- NOTE: For purposes of AE definition, study intervention (also referred to as Sponsor's product) includes any pharmaceutical product, biological product, vaccine, diagnostic agent, or protocol specified procedure whether investigational or marketed (including placebo, active comparator product, or run-in intervention), manufactured by, licensed by, provided by, or distributed by the Sponsor for human use in this study.

Events meeting the AE definition

- Any abnormal laboratory test results (hematology, clinical chemistry, or urinalysis) or other safety assessments (eg, ECG, radiological scans, vital signs measurements), including those that worsen from baseline, considered clinically significant in the medical and scientific judgment of the investigator.
- Exacerbation of a chronic or intermittent pre-existing condition including either an increase in frequency and/or intensity of the condition.

- New conditions detected or diagnosed after study intervention administration even though it may have been present before the start of the study.
- Signs, symptoms, or the clinical sequelae of a suspected drug-drug interaction.
- Signs, symptoms, or the clinical sequelae of a suspected overdose of either study intervention or a concomitant medication.
- For all reports of overdose (whether accidental or intentional) with an associated AE, the AE term should reflect the clinical symptoms or abnormal test result. An overdose without any associated clinical symptoms or abnormal laboratory results is reported using the terminology “accidental or intentional overdose without adverse effect.”
- Any new cancer (that is not a condition of the study). Progression of the cancer under study is not considered a reportable event unless it results in hospitalization or death.

Events NOT meeting the AE definition

- Medical or surgical procedure (eg, endoscopy, appendectomy): the condition that leads to the procedure is the AE.
- Situations in which an untoward medical occurrence did not occur (social and/or convenience admission to a hospital).
- Anticipated day-to-day fluctuations of pre-existing disease(s) or condition(s) present or detected at the start of the study that do not worsen.
- Surgery planned prior to informed consent to treat a pre-existing condition that has not worsened.
- Refer to Section 8.4.6 for protocol-specific exceptions.

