8.4 Adverse Events (AEs), Serious Adverse Events (SAEs), and Other Reportable Safety Events

The definitions of an AE or SAE, as well as the method of recording, evaluating, and assessing causality of AE and SAE and the procedures for completing and transmitting AE, SAE, and other reportable safety event reports can be found in Appendix 3.

Progression of the cancer under study is not considered an AE as described in Section 8.4.6 and Appendix 3.

Adverse events, SAEs, and other reportable safety events will be reported by the participant (or, when appropriate, by a caregiver, surrogate, or the participant's legally authorized representative).

The investigator and any designees are responsible for detecting, documenting, and reporting events that meet the definition of an AE or SAE as well as other reportable safety events. Investigators need to document if an SAE was associated with a medication error, misuse, or abuse. Investigators remain responsible for following up AEs, SAEs, and other reportable safety events for outcome according to Section 8.4.3.

The investigator, who is a qualified physician, will assess events that meet the definition of an AE or SAE as well as other reportable safety events with respect to seriousness, intensity/toxicity and causality.

8.4.1 Time Period and Frequency for Collecting AE, SAE, and Other Reportable Safety Event Information

- All AEs, SAEs, and other reportable safety events that occur after the participant provides documented informed consent but before intervention randomization must be reported by the investigator if the participant is receiving placebo run-in or other run-in treatment, if the event cause the participant to be excluded from the study, or is the result of a protocol-specified intervention, including but not limited to washout or discontinuation of usual therapy, diet, or a procedure.
- All AEs from the time of intervention randomization through 30 days following cessation of study intervention must be reported by the investigator.
- All AEs meeting serious criteria, from the time of intervention randomization through 90 days following cessation of study intervention or 30 days following cessation of study intervention if the participant initiates new anticancer therapy, whichever is earlier, must be reported by the investigator.

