8.4.6 Disease-related Events and/or Disease-related Outcomes Not Qualifying as AEs or SAEs

Efficacy endpoints as outlined in this section will not be reported to the Sponsor as described in Section 8.4.1.

Specifically, the suspected/actual events covered in this exception include any event that is disease progression of the cancer under study.

The Sponsor will monitor unblinded aggregated efficacy endpoint events and safety data to ensure the safety of the participants in the study. Any suspected endpoint that upon review is not progression of the cancer under study will be forwarded to Global Pharmacovigilance as an SAE within 24 hours of determination that the event is not progression of the cancer under study.

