10.3.3 Definition of SAE

If an event is not an AE per definition above, then it cannot be an SAE even if serious conditions are met.

An SAE is defined as any untoward medical occurrence that, at any dose:

a. Results in death

b. Is life-threatening

- The term “life-threatening” in the definition of “serious” refers to an event in which the participant was at risk of death at the time of the event. It does not refer to an event, which hypothetically might have caused death, if it were more severe.

c. Requires inpatient hospitalization or prolongation of existing hospitalization

- Hospitalization is defined as an inpatient admission, regardless of length of stay, even if the hospitalization is a precautionary measure for continued observation. (Note: Hospitalization for an elective procedure to treat a pre-existing condition that has not worsened is not an SAE. A pre-existing condition is a clinical condition that is diagnosed prior to the use of an MSD product and is documented in the participant's medical history.

d. Results in persistent or significant disability/incapacity

- The term disability means a substantial disruption of a person's ability to conduct normal life functions.
- This definition is not intended to include experiences of relatively minor medical significance such as uncomplicated headache, nausea, vomiting, diarrhea, influenza, and accidental trauma (eg, sprained ankle) that may interfere with or prevent everyday life functions but do not constitute a substantial disruption.

e. Is a congenital anomaly/birth defect

- In offspring of participant taking the product regardless of time to diagnosis.

f. Other important medical events

- Medical or scientific judgment should be exercised in deciding whether SAE reporting is appropriate in other situations such as important medical events that may not be immediately life-threatening or result in death or hospitalization but may jeopardize the participant or may require medical or surgical intervention to prevent 1 of the other outcomes listed in the above definition. These events should usually be considered serious.
- Examples of such events include invasive or malignant cancers, intensive treatment in an emergency room or at home for allergic bronchospasm, blood dyscrasias or convulsions that do not result in hospitalization, or development of drug dependency or drug abuse.

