10.3.5 Recording AE and SAE

AE and SAE recording

- When an AE/SAE occurs, it is the responsibility of the investigator to review all documentation (eg, hospital progress notes, laboratory, and diagnostics reports) related to the event.
- The investigator will record all relevant AE/SAE information on the AE CRFs/worksheets at each examination.
- It is not acceptable for the investigator to send photocopies of the participant's medical records to the Sponsor in lieu of completion of the AE CRF page.
- There may be instances when copies of medical records for certain cases are requested by the Sponsor. In this case, all participant identifiers, with the exception of the participant number, will be blinded on the copies of the medical records before submission to the Sponsor.
- The investigator will attempt to establish a diagnosis of the event based on signs, symptoms, and/or other clinical information. In such cases, the diagnosis (not the individual signs/symptoms) will be documented as the AE/SAE.

Assessment of intensity/toxicity

- An event is defined as “serious” when it meets at least 1 of the predefined outcomes as described in the definition of an SAE, not when it is rated as severe.
- The investigator will make an assessment of intensity for each AE and SAE (and other reportable safety event) according to the NCI CTCAE, version 5.0. Any AE that changes CTCAE grade over the course of a given episode will have each change of grade recorded on the AE CRFs/worksheets.
 - Grade 1: Mild; asymptomatic or mild symptoms; clinical or diagnostic observations only; intervention not indicated.
 - Grade 2: Moderate; minimal, local or noninvasive intervention indicated; limiting age-appropriate instrumental ADL.
 - Grade 3: Severe or medically significant but not immediately life-threatening; hospitalization or prolongation of hospitalization indicated; disabling; limiting self-care ADL.
 - Grade 4: Life threatening consequences; urgent intervention indicated.
 - Grade 5: Death related to AE.

Assessment of causality

- Did the Sponsor's product cause the AE?

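### Sections 10.3.2 and 8.4.6 disagree on whether melanoma progression leading to hospitalization or death is reportable, and Section 9.6.2 does not say how such events enter the AE summaries

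*Combined protocol and SAP*

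**What the plan says.** Four places bear on reporting.

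- **Section 10.3.2**, in the list of events that count as AEs: "Progression of the cancer under study is not considered a reportable event unless it results in hospitalization or death".
- **Section 8.4.6**, whose title says that such events do not qualify as AEs or SAEs: "the suspected/actual events covered in this exception include any event that is disease progression of the cancer under study". Their effect on reporting is also stated there: "Efficacy endpoints as outlined in this section will not be reported to the Sponsor as described in Section 8.4.1".
- **Section 8.4**, opening text: "Progression of the cancer under study is not considered an AE as described in Section 8.4.6 and Appendix 3".
- **Section 10.3.2** again, at the end of the list of events that do not count as AEs: "Refer to Section 8.4.6 for protocol-specific exceptions".

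Section 10.3.3 then makes AE status a precondition for SAE status: "If an event is not an AE per definition above, then it cannot be an SAE even if serious conditions are met".

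On the analysis side, Section 9.6.2 and Table 15 place any AE, any serious AE and any Grade 3 to 5 AE in Tier 2, where arms are compared with 95% confidence intervals. Individual Grade 3 to 5 AEs and SAEs enter Tier 2 once 2 participants in one arm have the event. Neither place says whether progression terms are counted.

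**The concern.** A site that follows the clause in Section 10.3.2 would report an admission or death from progression as an SAE. A site that follows Section 8.4.6 would not. Once reported, such an event would normally also be Grade 3 or higher, given the grading text in Section 10.3.5: "Grade 3: Severe or medically significant but not immediately life-threatening; hospitalization or prolongation of hospitalization indicated" and "Grade 5: Death related to AE".

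Two things are at stake in the safety comparison. If progression is counted, the serious and Grade 3 to 5 AE proportions carry part of the efficacy result, and the arm with less progression looks safer for that reason alone. If sites differ in their reading, the proportions also depend on the site. The trial is open-label (Section 6.3.3), so a site knows the arm when it decides whether to report.

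**Working it through.** The plan states no figure on this point, so there is none to reproduce. The check is a comparison of texts, followed by an illustration on assumed rates.

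**Texts side by side**

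| Place | Progression with hospitalization or death |
|---|---|
| 10.3.2, list of AEs | Reportable |
| 8.4.6 | Exempt, no exception |
| 8.4 | Not an AE, citing both 8.4.6 and Appendix 3 |
| 10.3.2, list of non-AEs | Points to 8.4.6 for exceptions |
| 10.3.3 | A non-AE cannot be an SAE |
| 9.6.2 and Table 15 | Silent |

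Section 10.3.3 does not settle the matter. It relies on the AE definition that precedes it, which is Section 10.3.2, where the disputed clause stands. The pointer to Section 8.4.6 favours exemption but does not withdraw the clause.

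**Inputs**

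- Arm size: 135 / 3 = 45 (Section 9.1). Early termination may make it smaller. One participant is 1/45 = 2.2 points.
- SAE window: randomization to 90 days after treatment stops, or 30 days if new anticancer therapy starts (Section 8.4.1).
- q = proportion of an arm with progression leading to hospitalization or death in that window. Not in the documents; assumed.
- b = proportion with an SAE from another cause, taken as equal in both arms. Not in the documents; assumed 20% to 50%.

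**Shift in the SAE difference**

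If the two kinds of event are independent, an arm's SAE proportion with progression counted is b + (1 − b)q. With equal b, the difference moves from 0 to (1 − b)(q in the combination arm − q in Arm 3). For q = 15% against 25%:

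| b | Calculation | Shift (points) |
|---|---|---|
| 20% | 0.80 × (−10) | −8 |
| 30% | 0.70 × (−10) | −7 |
| 40% | 0.60 × (−10) | −6 |
| 50% | 0.50 × (−10) | −5 |

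If no participant with a progression event has any other SAE, the shift is the full −10, which is the limit for these inputs. Other inputs at b = 30%:

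- 10% against 20%: −7 points
- 5% against 20%: −10.5 points
- 10% in both arms: 0

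The sign reverses if the combination arm has more progression events.

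**Scale**

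An approximate 95% half-width is 1.96 × √(2p(1 − p)/45), which gives 16.5 points at p = 20%, 19.7 at 35% and 20.7 at 50%. This is a Wald approximation; the plan uses Miettinen and Nurminen. Against it, the shift is 8/16.5 = 48% of a half-width at the 20% rate and 5/20.7 = 24% at the 50% rate.

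**Progression as a Tier 2 row of its own**

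The threshold is 2/45 = 4.4% (the plan says about 5%). If sites report these events under one term, P(at least 2 of 45) = 1 − (1 − q)^45 − 45q(1 − q)^44:

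| q | P(at least 2) |
|---|---|
| 2% | 0.23 |
| 5% | 0.67 |
| 10% | 0.95 |

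**The case against.** The best answer is that the documents already lean one way. Section 8.4 says without qualification that progression is not an AE. Section 8.4.6 says the same in its title and text. The pointer to it stands in the list of non-AEs, and Section 10.3.3 bars a non-AE from being an SAE. A site that reads Appendix 3 to the end is steered away from reporting. This stands, and it lowers the likely number of affected events. A reader might infer that neither section has the better claim, or that the rates are bound to differ by site. The documents support only the weaker statement that sites may differ, because the clause remains and nothing overrides it.

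Section 8.4.6 also has the Sponsor review endpoint events and pass on as SAEs those found not to be progression. That is a real safeguard, but it works in one direction. It does not take out progression that a site reported under Section 10.3.2.

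A reader might further infer that toxicity from V937 would be hidden. The documents do not support that. Table 15 has separate drug-related categories (any, serious, Grade 3 to 5), which progression would rarely enter. Progression reported by 2 or more participants in an arm would appear as its own row. Section 9.6.2 states no safety hypotheses and treats the intervals as descriptive. The direction of any distortion also assumes that V937 reduces progression, which is what the trial is testing.

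**Conclusion.** The inconsistency is real and stands in the current text. Its consequence is limited to the descriptive Tier 2 comparisons of any AE, any serious AE and any Grade 3 to 5 AE, which could include efficacy events to an extent that varies by site. The drug-related categories should be little affected; ORR, PFS and OS are unaffected.

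The size cannot be found from the documents. On the assumed 15% and 25%, with 45 per arm, equal other-cause SAE rates of 20% to 50%, independence, and every such event reported, the SAE difference moves by about 8 down to 5 points. A reader might take the 10-point limit as the expected effect. It is not: it requires that no participant has both kinds of event, and the inputs themselves are assumptions. If most sites follow Section 8.4.6, the shift is smaller. If they follow different rules, it depends on which sites saw the events. If early termination leaves fewer than 45 per arm, each reclassified participant counts for more than 2.2 points.

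**What to change.** 1. Reconcile Sections 8.4, 8.4.6 and 10.3.2 (both the clause and the pointer) so that one reporting rule applies. Which rule that should be is for the sponsor to decide; the review asks only that the texts agree.
2. Add to Section 9.6.2: events recorded as progression of the melanoma under study are excluded from the AE, SAE and Grade 3 to 5 summaries and listed separately by arm, whichever way the site reported them.

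The second change matters more for the analysis. The study is being discontinued, and new reporting text cannot harmonize events already recorded. Exclusion can be applied alike to sites that reported progression and sites that did not, whereas events never reported as SAEs cannot be restored to the AE data. For the same reason, the separate listing should be labelled as possibly incomplete.

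The cost is a few words in the reporting sections and one sentence in Section 9.6.2. No new data are needed and no efficacy analysis changes.
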